Clinical Trial Protocol: APD334-003

Study Title: A Phase 2, Randomized, Double-Blind, Placebo-Controlled, Parallel Group, Multi-Center Study to Investigate the Safety and Efficacy of APD334 in Patients with Moderately to Severely Active Ulcerative Colitis

Study Number: APD334-003

Study Phase: 2

Product Name: APD334

IND Number: 125,154

EudraCT Number: 2015-001942-28

Indication: Ulcerative Colitis

Investigators: Multicenter

Sponsor: Arena Pharmaceuticals, Inc.
[name]
[name]

	Date
Original Protocol:	08 April 2015
Amendment 01:	01 May 2015
Amendment 02:	17 June 2015
Amendment 03:	30 June 2015
Amendment 04:	21 September 2015
Amendment 05:	10 October 2016
Amendment 06:	27 March 2017

Confidentiality Statement

This document contains confidential information of Arena Pharmaceuticals, Inc. Unauthorized distribution, copying, or disclosure is strictly prohibited unless required by applicable law. Persons receiving this information must be notified that it is confidential and may not be further disclosed.

NCT Number: NCT02447302
This NCT number has been applied to the document for
purposes of posting on clinicaltrials.gov

[figure not shown]

PROTOCOL AMENDMENT SUMMARY

The following is a list of **major** changes made to the APD334-003 Protocol Amendment 05 dated 10 October 2016. Minor clarifications and corrections have been made throughout for consistency. These changes are incorporated in Protocol Amendment 06 dated 27 March 2017.

Section(s) Amended	Description of Changes Made
Header/Footer, Title Page, and TOC	Added "Amendment 06", updated date to reflect finalization of amended protocol, updated pagination and TOC.
Protocol Amendment Summary	Updated table to include summary of changes to the protocol.
Synopsis	Updated sponsor contact details
Synopsis	
Changed Primary Objective "The primary objective will be to determine the effect of treatment with APD334 in inducing clinical remission at 12 weeks" to:
 
Current "The primary objective of this proof-of-concept study is to determine the effect of treatment with APD334 in improving 3-component Mayo Clinic Score (score ranging from 0 to 9, including stool frequency, rectal bleeding and findings on endoscopy) at Week 12"

Synopsis	
Added the following Secondary Objectives:
 
 • To determine the effect of treatment with APD334 on a combination of clinical remission and clinical response reflected by a composite endpoint at 12 weeks • To determine the effect of treatment with APD334 in inducing clinical remission at 12 weeks
Synopsis	
Added the following Exploratory Objectives:
 
 • to determine the effect of APD334 treatment on Total Mayo Clinic Score at 12 weeks. 

[figure not shown]
Synopsis	
Study Design: Changed the study description: “phase 2, dose-ranging, placebo-controlled clinical study” to:
 
Current “phase 2, proof-of-concept and dose-ranging, placebo-controlled clinical study”
 
Changed patients with the option to enroll in an extension study APD334-005: “responder patients” to: Current “all patients”

Synopsis	
Changed Primary Efficacy Endpoints “The proportion of patients achieving clinical remission [defined as individual subscores of the 3-component Mayo Clinic score as follows: an endoscopy score (using flexible proctosigmoidoscopy) of 0 or 1, a rectal bleeding score of 0, and a stool frequency score of 0 or 1 with a decrease of ≥ 1 point from baseline subscore at Week 12” to:
 
Current “
 
 • The improvement of 3-component Mayo Clinic Score (score ranging from 0 to 9, including stool frequency, rectal bleeding and findings on endoscopy) at Week 12.”
Synopsis	
Added the following Secondary Efficacy Endpoints:
 
 • The trichotomous composite endpoint of clinical remission and clinical response (score ranging 0 to 2: score 2 for achieving both clinical remission and clinical response; 1 for achieving only clinical response, and 0 for achieving neither) at Week 12 • The proportion of patients achieving clinical remission [defined as individual subscores of the 3-component Mayo Clinic score as follows: an endoscopy score (using flexible proctosigmoidoscopy) of 0 or 1, a rectal bleeding score of 0, and a stool frequency score of 0 or 1 with a decrease of ≥ 1 point from baseline subscore at Week 12
Synopsis	
Added the following Exploratory Objectives:
 
 • Improvement in Total Mayo Clinic Score (score ranging from 0 to 12, including stool frequency, rectal bleeding and findings on endoscopy, and physician’s global assessment) at Week 12

[figure not shown]

	
Synopsis	Data Analysis section updated to reflect new primary, secondary and exploratory Endpoints.
Study Definition	Added “Trichotomous composite endpoint” definition
2. Study Objectives	Updated Primary and Secondary Objectives according to changes highlighted in the Synopsis.
3.1 Overall Study Design and Plan	
Study Design:
 
Changed the study description: “phase 2, dose-ranging, placebo-controlled clinical study” to: Current “phase 2, proof-of-concept and dose-ranging, placebo-controlled clinical study”
 
Changed patients with the option to enroll in an extension study APD334-005: “responder patients” to: Current “all patients (responders and non-responders)”

4.2 Inclusion Criteria
	

4.3 Exclusion Criteria
	

6.12.1 Permitted Medications for the Treatment of UC
	
Changed “for the 4 weeks immediately prior to screening” to: Current “for the 4 weeks immediately prior to screening endoscopy assessment”

6.15 Study and Site Discontinuation
	
Added section 6.15 to provide reasons to terminate the study or replace a site.

9 Planned Statistical Methods
	
Added specifications related to the intention of Section 9.

9.1.1 Hypotheses and Objectives
	
Primary, Secondary and Exploratory Objectives and Hypothesis were updated to reflect the updated Primary, Secondary and Exploratory Endpoints.

9.5 Efficacy Endpoints	Primary, Secondary and Exploratory Efficacy Endpoints were updated reflecting the changes highlighted in the Synopsis amendment summary section.
9.6.1 Primary, Secondary and Exploratory Efficacy Analysis	Primary, Secondary and Exploratory Efficacy Analysis were updated reflecting the changes highlighted in the Primary, Secondary and Exploratory Endpoints section.
9.6.3 Multiplicity	Updated to reflect the new Primary, Secondary and Exploratory Endpoints. Removal of Figure 1 – Statistical testing procedure in the UC Trial

Appendix 3 Mayo Clinic Score – SAMPLE101

[figure not shown]
SYNOPSIS

[figure not shown]
[figure not shown]

Name of Drug:	APD334
Indication:	Ulcerative Colitis
Sponsor:	Arena Pharmaceuticals, Inc. [name] [name]
Name of Sponsor Contact:	[REDACTED] Arena Pharmaceuticals, Inc [name] [name] Phone [REDACTED] [REDACTED]
Name of Principal Investigator(s):	Multi-center
Medical Monitor:	[REDACTED] Arena Pharmaceuticals, Inc. Phone: [REDACTED] Mobile: [REDACTED] [REDACTED]
Test Product, Dose and Mode of Administration:	
 • 1 mg APD334 once daily (q.d.) for 12 weeks • 2 mg APD334 once daily (q.d.) for 12 weeks • Placebo once daily (q.d.) x 12 weeks 
The route and mode of administration of APD334 and placebo capsules will be oral with an adequate amount of water (240 mL).

Concurrent Control:	Placebo; microcrystalline cellulose in hard gelatin capsules
Objectives:	
Primary Objective: The primary objective of this proof-of-concept study is to determine the effect of treatment with APD334 in improving 3-component Mayo Clinic Score (score ranging from 0 to 9, including stool frequency, rectal bleeding and findings on endoscopy) at Week 12

	
Secondary Objectives: The secondary objectives of this study are:
 
• To determine the effect of treatment with APD334 on a combination of clinical remission and clinical response reflected by a composite endpoint at 12 weeks• To determine the effect of treatment with APD334 in inducing clinical remission at 12 weeks• To determine the effect of treatment with APD334 in inducing clinical response at 12 weeks• To determine the effect of treatment with APD334 on endoscopic improvement at 12 weeks 
Safety Objective: The safety objective of this study is to determine the safety profile and tolerability of APD334 induction treatment.
 
Exploratory Objectives: The exploratory objectives of the study are:
 
• to determine the effect of APD334 treatment on Total Mayo Clinic Score at 12 weeks. 
--	---

	
Study Design:	
This phase 2, proof-of-concept and dose-ranging, placebo-controlled clinical study will test 2 doses of APD334 or placebo in up to 240 patients with moderately to severely active ulcerative colitis.  will be randomized into a double-blind, placebo-controlled study, receiving one of 2 doses of APD334 or matching placebo for 12 weeks.
 
Treatment arms will consist of once daily (q.d.) doses of 1 mg APD334, 2 mg APD334, or matching placebo. Patients will be randomized in a 1:1:1 ratio and will be stratified by presence or absence of current oral corticosteroid usage and previous exposure to TNFα antagonists.
 
Entry criteria will be based on confirmation of moderately to severely active UC, as defined by a 3-component Mayo Clinic 

	
At the end of the study all patients will have the option to enroll in an extension of the study (APD334-005) following completion of all study procedures and providing they meet all inclusion criteria for the extension study.
 
Patients who do not participate in the extension study (APD334-005) will have a 2-week follow-up visit after the last clinical visit.

Study Site(s):	This study will be conducted in approximately 100 clinical centers worldwide.
Patient Population:	
Duration per Patient:	
~18 weeks: ~28 days of screening, followed by a 12-week induction period. Patients who do not participate in the APD334-005 extension study will have a 2-week follow-up visit after the last clinical visit.
 
Clinic visits will occur during the screening period (to be completed up to ~28 days before first dose of study medication) and approximately every 2-4 weeks during the study. Additional visits may occur at the discretion of the investigator.

Patient Assignment:	Eligible patients will be randomized in a 1:1:1 ratio to receive once daily (q.d.) doses of 1 mg APD334, 2 mg APD334, or matching placebo.
Sample Size:	Up to 240 patients total.
Efficacy Endpoints	
Primary:
 
 The improvement of 3-component Mayo Clinic Score (score ranging from 0 to 9, including stool frequency, rectal bleeding and findings on endoscopy) at Week 12. 
Secondary:
 
 The trichotomous composite endpoint of clinical remission and clinical response (score ranging 0 to 2: score 2 for achieving both clinical remission and clinical response; 1 for achieving only clinical response, and 0 for achieving neither) at Week 12

	
• The proportion of patients achieving clinical remission [defined as individual subscores of the 3-component Mayo Clinic score as follows: an endoscopy score (using flexible proctosigmoidoscopy) of 0 or 1, a rectal bleeding score of 0, and a stool frequency score of 0 or 1 with a decrease of ≥ 1 point from baseline subscore at Week 12• The proportion of patients who achieve clinical response [defined as a decrease in the 3-component Mayo Clinic score of ≥ 2 points and a decrease of $\geq 30\%$ with either a decrease of rectal bleeding of ≥ 1 or rectal bleeding score of 0 or 1] at Week 12• The proportion of patients who achieve endoscopic improvement [defined as Mayo endoscopic subscore (using findings of flexible proctosigmoidoscopy) of ≤ 1 point] at Week 12 
Exploratory:
 
• Improvement in Total Mayo Clinic Score (score ranging from 0 to 12, including stool frequency, rectal bleeding and findings on endoscopy, and physician's global assessment) at Week 12 
--	--

	
Safety Assessments:	
• Physical examinations including ophthalmoscopy (and optical coherence tomography [OCT], where available)• Clinical laboratory tests to include hematology, serum chemistry, coagulation, and urinalysis• Vital sign measurements• Pulmonary Function Tests (PFTs)• 12-lead electrocardiograms (ECGs)• Adverse event reporting
	

	
Data Analyses:	
The primary analysis will be based on the change of 3-component Mayo Clinic Score at Week 12 from baseline using an analysis of covariate (ANCOVA) model with terms for treatment, current oral corticosteroid use, prior exposure to TNFα antagonists and baseline value as covariate. Least-squares mean (LSM) by treatment group and its 95% confidence interval (CI), and least-squares mean difference between treatment group and its 95% CI will be reported.
 
The secondary analyses include following:
 
• Trichotomous composite endpoint of clinical remission and clinical response at Week 12 is an ordinal categorical endpoint with 3 categories (2, 1, 0). It will be analyzed using Cochran-Mantel-Haenszel method adjusted for the stratification factors of presence or absence of current oral corticosteroid therapy at baseline and previous exposure to TNFα antagonists. The testing statistic will be computed using modified ridit score for between-treatment comparison.• The proportion of patients who achieve clinical remission, clinical response, or endoscopic improvement will be analyzed individually using Cochran-Mantel-Haenszel (CMH) test adjusted for the stratification factors of presence or absence of current oral corticosteroid therapy at baseline and previous exposure to TNFα antagonists, to compare the difference of proportions between treatment group. The CMH stratified risk difference and its 95% confidence interval will be provided 
Mayo Clinic Score data handling: for each visit during the study (excluding the screening/baseline visit which uses 10 prior days), stool frequency and rectal bleeding subscores will be derived from electronic patient diaries completed over the 7 days prior to a study visit. Note that the day prior, day of and day after proctosigmoidoscopy will not be used for patient diary entry because of the required bowel prep for the procedure. These subscores will be calculated using the following rules:

	
1. The scores from the 3 most recent days prior to the actual day of the study visit will be averaged and rounded to the nearest integer.2. If patient diary entries from 3 days are not available, the scores from the 2 most recent entries will be averaged and rounded to the nearest integer.3. If less than 2 days of diary data are available, the subscore will be considered missing. 
All patients who prematurely discontinue for any reason will be considered failures (non-responders) for all the proportion based endpoints.
 
Exploratory efficacy analyses:
  
Dose response analyses will be performed using ANCOVA model for continuous variables, or logistic regression model for categorical variables, as appropriate. Treatment group and appropriate baseline covariates will be included in the analysis model. Statistical testing of dose response trend will be based on appropriate contrast statement assuming monotonic dose response profile in placebo, APD334 low dose and APD334 high dose.
 
A statistical testing procedure will be constructed to manage multiplicity issues concerning primary and secondary efficacy analyses in order to control overall Type I error rate for efficacy testing not exceeding 0.05. The details of testing procedure will be specified in a separate Statistical Analysis Plan.
 
For the comparison of the proportion of patients who achieve clinical remission between APD334 versus placebo, a sample of ~80 patients per group will provide 80% power to detect a difference of 18% (from 10% to 28%) at $\alpha=5\%$ (2-sided test). This calculation is based upon an assumed placebo rate of 10%.
 
Safety information after administration of multiple doses of APD334 in patients with moderately to severely active ulcerative colitis will be evaluated by tabulating adverse experiences and clinical assessment of clinical laboratory data.

Date:	27 March 2017

[figure not shown]
LIST OF ABBREVIATIONS

µg	microgram
ABPM	ambulatory blood pressure monitor
ADL	Activities of Daily Living
ALB	albumin
ALK-P	alkaline phosphatase
ALT	alanine aminotransferase (SGPT)
ANOVA	analysis of variance
AST	aspartate aminotransferase (SGOT)
bpm	beats per minute
BUN	blood urea nitrogen
Ca	calcium
CBC	complete blood count (test)
CFR	Code of Federal Regulations
CGMP	Current Good Manufacturing Practice
CI	confidence interval
CIA	collagen-induced arthritis
Cl	chloride
CL/F	apparent oral clearance
CL _r	renal clearance
CRF	case report form
CRO	contract research organization
DSMB	Data Safety Monitoring Board
EAE	experimental autoimmune encephalomyelitis
ECG	electrocardiogram
eCRF	electronic CRF
ED ₅₀	median effective dose
ELISA	enzyme-linked immunosorbent assay
FDA	Food and Drug Administration
FEF _{25-75%}	mean forced expiratory flow between 25 and to 75% of FVC
FEV ₁	forced expiratory volume in the first second
FVC	forced vital capacity
GCP	Good Clinical Practice
GGT	gamma glutamyl transferase
Hb	hemoglobin
HBsAg	hepatitis B surface antigen

hCG	human chorionic gonadotropin
Hct	hematocrit
HCV	hepatitis C virus
HDPE	High-density polyethylene
HIV	human immunodeficiency virus
h	hour
HR	heart rate
█	█
ICH	International Conference on Harmonisation
IEC	Independent Ethics Committee
IND	Investigational New Drug
IRB	Institutional Review Board
INR	International Normalized Ratio
kg	kilogram
LDH	lactate dehydrogenase
MCH	mean corpuscular hemoglobin
MCS	Mayo Clinic score
MCV	mean corpuscular volume
MedDRA	Medical Dictionary for Regulatory Activities
mg	milligram
mL	milliliter
mm	millimeter
mmHg	millimeters of mercury
█	█
MRSD	maximum recommended starting dose
Na	sodium
NOAEL	no observed adverse effect level
OCT	optical coherence tomography
OTC	over-the-counter
PA	posteroanterior
PD	pharmacodynamic
PBL	peripheral blood lymphocyte
PFT	pulmonary function test
PI	Principal Investigator
█	█
PML	progressive multifocal leukoencephalopathy
PRO	patient reported outcome

PT	prothrombin time
PTT	partial thromboplastin time
RBC	red blood cell (count)
RIBA	recombinant immunoblot assay
S1P(1-5)	sphingosine 1-phosphate (1-5) receptor
SAE	serious adverse event
SAS	statistical analysis software
SBP	systolic blood pressure
SD	standard deviation
sec	second
SOP(s)	standard operating procedure(s)
T _{EM}	T effector memory cells
VICF	Voluntary Informed Consent Form
VS	vital signs
WBC	white blood cell (count)
WHO	World Health Organization
WHODRUG	World Health Organization Drug Dictionary

STUDY DEFINITIONS

Term	Definition
Mayo Clinic score (Complete Mayo or MCS)	Instrument designed to measure disease activity of ulcerative colitis consisting of 4 subscores: stool frequency, rectal bleeding, findings of flexible proctosigmoidoscopy, and physician global assessment with each component ranging from 0 to 3 (0=normal, 1=mild, 2=moderate, 3=severe). Total score therefore ranges from 0 to 12, with a higher score indicating more severe disease.
3-component Mayo Clinic score	Consists of 3 of the 4 subscores found in the complete Mayo Clinic score as follows: stool frequency, rectal bleeding, findings of flexible proctosigmoidoscopy. Total score range: 0 to 9, each component ranging from 0 to 3 (0=normal, 1=mild, 2=moderate, 3=severe).
	
Physician's global assessment	The physician's global assessment acknowledges the three other criteria findings of the Mayo Clinic score; the patient's daily record of abdominal discomfort and general sense of well-being, and other observations, such as physical findings and the patient's performance. Total score range: 0 to 3 (0=normal, 1=mild, 2=moderate, 3=severe).
Clinical Response	Decrease in the 3-component Mayo Clinic score of ≥ 2 points and a decrease of $\geq 30\%$ with either a decrease of rectal bleeding of ≥ 1 or rectal bleeding score of 0 or 1 at Week 12.
Clinical Remission	Individual subscores of the 3-component Mayo Clinic score as follows: an endoscopy score (using flexible proctosigmoidoscopy) of 0 or 1, a rectal bleeding score of 0, and a stool frequency score of 0 or 1 with a decrease of ≥ 1 point from baseline at Week 12.
Trichotomous composite endpoint	An ordinal categorical endpoint with 3 scores: score 2 for achieving both clinical remission and clinical response, 1 for achieving only clinical response, 0 for achieving neither.

Term	Definition
Endoscopic Improvement	Mayo endoscopic subscore (using findings of flexible proctosigmoidoscopy) of ≤ 1 point at Week 12.
Intolerable AE	Adverse event leading to study drug discontinuation.

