3.1 Overall Study Design and Plan

[figure not shown]
APD334-003 is a phase 2, proof-of-concept and dose ranging clinical study designed to test the ability of APD334 to induce clinical response and/or remission in patients with moderately to severely active ulcerative colitis. Up to 240 eligible patients will be randomized into a double-blind, placebo-controlled study to receive once daily (q.d.) doses of APD334 (1 mg or 2 mg) or matching placebo in a 1:1:1 ratio for 12 weeks. The screening period for the study is up to ~28 days which includes several assessments that must be completed within 10 days prior to randomization to ensure eligibility for the study. Patient's vital signs will be monitored using a Holter monitor for up to 24 hours pre-dose through 24 hours post dose. Patients will report daily stool frequency and rectal bleeding using an electronic device throughout the study and will be scheduled at regular intervals for safety, [REDACTED], and efficacy assessments. A 34-week extension study (APD334-005) is offered to all patients (responders and non-responders) who complete the study and will meet the relevant eligibility criteria. Patients who do not participate in the extension study or who have discontinued prematurely from the study will have a 2-week follow-up visit after the last clinical visit.

[figure not shown]

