9.5 Efficacy Endpoints

Primary:

- The improvement of 3-component Mayo Clinic Score (score ranging from 0 to 9, including stool frequency, rectal bleeding and findings on endoscopy) at Week 12.

[figure not shown]
Secondary:

- The trichotomous composite score of clinical remission and clinical response (score ranging 0 to 2: score 2 for achieving both clinical remission and clinical response; 1 for only achieving clinical response, and 0 for achieving neither) at Week 12.
- The proportion of patients achieving clinical remission [defined as individual subscores of the 3-component Mayo Clinic score as follows: an endoscopy score (using flexible proctosigmoidoscopy) of 0 or 1, a rectal bleeding score of 0, and a stool frequency score of 0 or 1 with a decrease of ≥ 1 point from baseline subscore at Week 12]
- The proportion of patients who achieve clinical response [defined as a decrease in 3-component Mayo Clinic score of ≥ 2 points and a decrease of $\geq 30\%$ with either a decrease of rectal bleeding of ≥ 1 or rectal bleeding score of 0 or 1] at Week 12

- The proportion of patients who achieve endoscopic improvement [defined as Mayo endoscopic subscore (using findings of flexible proctosigmoidoscopy) of ≤ 1 point] at Week 12

Exploratory:

- Improvement in Total Mayo Clinic Score (score ranging from 0 to 12, including stool frequency, rectal bleeding and findings on endoscopy, and physician's global assessment) at Week 12

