9.6.3 Multiplicity

[figure not shown]
A statistical testing procedure will be constructed to manage multiplicity issues concerning primary and secondary efficacy analyses in order to control overall Type I error rate for efficacy testing not exceeding 0.05. The details of testing procedure will be specified in a separate SAP.

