6.3 Multiplicity

Primary comparison is between APD334 2 mg vs placebo [REDACTED]

The primary analysis will compare PMS#1 change from baseline between treatment groups using a one-sided test at the 0.05 level of significance and 90% CI will be reported. If the result is significant, the primary hypothesis will be considered satisfied and this study will be declared positive. If this primary test is significant the secondary testing will proceed as following.

[figure not shown]
Secondary endpoints:

1. Proportion of patients who achieve endoscopic improvement at Week 12
2. Improvement in 2 component Mayo score (score ranging from 0 to 6, including rectal bleeding and findings on endoscopy) at Week 12
3. Improvement in Total Mayo Clinic Score (score ranging from 0 to 12, including stool frequency, rectal bleeding and findings on endoscopy, and physician's global assessment) at Week 12.

If the primary testing is significant, testing for secondary endpoints will proceed in pre-specified order. Provided that all previously specified tests are statistically significant ($p < 0.05$), each of these comparisons will be assessed using the one-sided test at the 0.05 level of significance. However, if a comparison is not statistically significant, then subsequent comparison(s) will be considered exploratory.

Exploratory endpoints:

- The trichotomous composite endpoint of clinical remission and clinical response (score ranging 0 to 2: score 2 for achieving both clinical remission and clinical response; 1 for achieving only clinical response, and 0 for achieving neither) at Week 12.
- The proportion of patients achieving clinical remission at Week 12
- Proportion of patients who achieve clinical response at Week 12

Non-formal statistical testing on treatment effect will be performed and reported along with nominal p-values.

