9 CHANGES IN THE PLANNED ANALYSIS FROM THE PROTOCOL

[figure not shown]
The following secondary objective and endpoint have been added to the SAP in comparison with Protocol Amendment #6:

1. 2-Component Mayo Clinic Score

The following changes to the secondary objectives and endpoints have been made:

1. The order has been changed to: Endoscopic Improvement, 2-Component Mayo Score and Total Mayo Score
2. Other objectives/endpoints previously listed as secondary (i.e. Trichotomous score, Clinical remission and Clinical response) are considered to be exploratory

The following exploratory objectives and endpoints have been added to the SAP in comparison with Protocol Amendment #6:

In addition, a change to the sample size calculation in comparison with Protocol Amendment #6 has been made:

Rationale for sample size calculation change:

In Protocol Amendment 06, the primary objective was changed to reflect a broad examination of potential clinical improvement across three domains (stool frequency, rectal bleeding, and endoscopic results), which is appropriate for a proof-of-concept study. The current endpoint is more sensitive to detecting clinically important differences between two doses of APD334 and placebo compared to a dichotomous complete remission endpoint.

The 95% CIs have been changed to 90% CIs for all analyses in comparison with Protocol Amendment #6.

The clinical remission definition has been updated to include “a rectal bleeding score of 0 or 1” in comparison with Protocol Amendment #6.

The clinical response definition has been updated as “a patient has achieved clinical response if he/she meets criteria of clinical remission, or meet criteria of clinical response defined in the protocol.”

The following change to the primary efficacy analysis has been made:

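### SAP 6.3 leaves three of the protocol's four secondary endpoints with nominal p-values only, although adding them at the end of the fixed sequence would cost no alpha

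*Protocol*

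**What the plan says.** **Protocol.** Section 9.5 lists four secondary endpoints, starting with "The trichotomous composite score of clinical remission and clinical response", then clinical remission, clinical response and endoscopic improvement. The Synopsis (Data Analyses) and Section 9.6.3 promise that "A statistical testing procedure will be constructed to manage multiplicity issues concerning primary and secondary efficacy analyses", so as to "control overall Type I error rate for efficacy testing not exceeding 0.05". Section 9.6.3 leaves its construction to the SAP: "The details of testing procedure will be specified in a separate SAP". Section 3.1 describes the study as "designed to test the ability of APD334 to induce clinical response and/or remission".

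**SAP.** Section 6.3 names 2 mg vs placebo as the primary comparison; the text after that is redacted. The visible sequence is the 3-component Mayo score, then endoscopic improvement, the 2-component Mayo score and the Total Mayo score, each at one-sided 0.05, stopping at the first failure: "If the primary testing is significant, testing for secondary endpoints will proceed in pre-specified order". For the trichotomous score, remission and response it says: "Non-formal statistical testing on treatment effect will be performed and reported along with nominal p-values". Section 9 records the reclassification: "Other objectives/endpoints previously listed as secondary (i.e. Trichotomous score, Clinical remission and Clinical response) are considered to be exploratory".

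**The concern.** Three of the four endpoints that the protocol placed in its error-controlled family are outside the SAP's formal testing. However strong the data, the trial cannot draw an error-controlled conclusion on remission or response, which Protocol 3.1 puts at the centre of the design.

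Two of the three formal secondary steps lie close to the primary. The 2-component score is the primary score without stool frequency, and the Total Mayo score is the primary score plus the physician's global assessment. The protocol does not list the 2-component score as an endpoint, and it lists the Total Mayo score as exploratory. SAP 1.2.4 gives medical reasons for the endpoints it chose. No visible text says why the other three had to leave the sequence.

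**Working it through.** **1. Endpoint status side by side**

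| Endpoint | Protocol 9.5 | SAP 4.1 and 6.3 |
|---|---|---|
| Trichotomous score | Secondary | Exploratory, nominal p |
| Clinical remission | Secondary | Exploratory, nominal p |
| Clinical response | Secondary | Exploratory, nominal p |
| Endoscopic improvement | Secondary | Secondary, formal step |
| 2-component Mayo score | Not listed | Secondary, formal step |
| Total Mayo score | Exploratory | Secondary, formal step |

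**2. The plans' own sample sizes**

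- SAP 7.1 (difference 1.15, SD 2.03, one-sided 5%, 80% power): n = 2 × (1.645 + 0.842)² × 2.03² / 1.15² = 38.5, so 39 per group. Power at 39 is 80.4% (normal) or 79.8% (t-test). The figure reproduces, and 3 × 39 = 117.
- Protocol 9.2 (10% vs 28%, about 80 per group, two-sided 5%): power is 83.3% by the normal approximation and 79.5% by Fisher's exact test. The stated 80% reproduces with Fisher's test.

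**3. Alpha cost of appending three steps**

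In a fixed sequence, a false rejection requires rejecting the first true null hypothesis in the order. That hypothesis is tested once, at 0.05. So the family-wise error is at most 0.05 for any number of steps and any correlation. Steps 1 to 4 are tested before steps 5 to 7 and do not depend on them, so their level and power are unchanged.

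Simulation check (300,000 runs per setting, one-sided z tests, common correlation 0, 0.3, 0.6 and 0.9, first true null at every possible position): family-wise error was 0.049 to 0.051 with the current 4 steps and 0.049 to 0.051 with 7 steps.

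**4. Stand-alone power for remission at the SAP's sample size**

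Inputs: 39 per arm (SAP 7.1), 10% vs 28% (Protocol 9.2), one-sided 0.05 (SAP 6.3). Mean rate 0.19.

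- SE under the null = √(2 × 0.19 × 0.81 / 39) = 0.0888
- SE under the alternative = √((0.10 × 0.90 + 0.28 × 0.72) / 39) = 0.0865
- Power = Φ((0.18 − 1.645 × 0.0888) / 0.0865) = Φ(0.39) = 0.65

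**5. What that means late in the sequence**

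Remission can be claimed only if every earlier step also succeeds, so 0.65 is a ceiling. As an illustration, put remission sixth, after the trichotomous score. The documents do not give most of the inputs, so these are assumptions: power 80% for each of the three score tests, 65% to 80% for endoscopic improvement, 70% for the trichotomous score, 65% for remission, and common correlation 0.3 to 0.8. The chance of a formal remission result is then about 28% to 54%.

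**6. Definitions differ**

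The protocol's remission requires a rectal bleeding score of 0. SAP 4.1 allows 0 or 1, and counts any remission as a response; Section 9 declares both changes. The 10% and 28% rates accompany the protocol's definition.

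**The case against.** The strongest reply is that this is a declared and delegated choice. The protocol leaves the testing procedure to the SAP. SAP Section 9 states the reclassification, and Sections 1.2.4, 4.1, 6.3 and Appendix 2 apply it consistently. The primary objective is the 3-component score, and Protocol 2.2 explains that a dichotomous remission endpoint is less sensitive. SAP 1.2.1 describes the design in terms of safety and efficacy, without Protocol 3.1's wording. A proof-of-concept trial may choose what it tests formally. All of this stands: a reader might infer an alpha breach or a hidden contradiction, and the documents support neither.

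A reader might also infer that the three nominal tests inflate the false-positive rate. With three true nulls, the chance of at least one one-sided p < 0.05 is 1 − 0.95³ = 14.3% if the tests are independent, and less if they are positively correlated. That is not a measure of harm here. The SAP labels this testing non-formal and makes no claim from it, and the fix changes no p-value. Under a global null the primary usually fails and the same nominal p-values are reported either way.

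The overlap argument also cuts both ways. Remission, response and the trichotomous score are built from the same three subscores as the primary, so they are not independent evidence either. Finally, the protocol's list is not stated to be a testing hierarchy, so its order is only one reasonable choice.

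None of this identifies a downside to appending the steps. The redaction in SAP 6.3 does not create one, provided the new steps follow everything already in the sequence.

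**Conclusion.** The point holds as an avoidable limitation, not as an error. Three protocol secondary endpoints lose any route to an error-controlled conclusion, and restoring that route costs no alpha and no power for existing tests. The family-wise error stays at one-sided 0.05 with four or seven steps.

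This rests on the order being fixed before unblinding and on each added step being tested only if all earlier ones succeed. The benefit exists only when the whole current sequence is significant. The 65% is stand-alone power for remission under the protocol's definition and rates; power at the actual step can only be equal or lower, and the rates under the SAP's broader definition are not given.

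The protocol's power statement is two-sided and the SAP's testing one-sided; the added steps neither cause nor cure that difference.

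**What to change.** Before database lock:

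- In SAP 6.3, extend the fixed sequence for 2 mg vs placebo after the Total Mayo score and after any other step already in it. Add the three endpoints in one stated order, for example the protocol's listing order: trichotomous score, remission, response. Test each at one-sided 0.05, and only if every earlier step is significant.
- State which remission and response definitions these steps use, the protocol's or the SAP's, and use the same ones in the trichotomous score.
- Align SAP 1.2.4, 4.1 and Appendix 2, and update Section 9.
- Keep nominal reporting for any step not reached.

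Cost: a few lines of SAP text. No patients, no new data, and no alpha taken from the primary or the existing secondary tests.
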